#### A3a. Financial Conflict of Interest

Does any member of study personnel (Investigator (including investigator's spouse and/or dependent children)) that are involved in the design, conduct, or reporting of the research have a Significant Financial Interest (SFI) that would reasonably appear to be affected by the research for which funding is sought and/or associated with an entity/business that would reasonably appear to be affected by the research?

No

#### **A5. Funding Source:**

Organization: PATIENT-CENTERED OUTCOMES RESEARCH INSTITUTE (PCORI)

#### **A6b. Research conducted outside of the United States:**

Country:  
Facility/Institution:  
Contact/Investigator:  
Phone Number:

If documentation of assurances has not been sent to the Office of Research, please explain:

#### **A7. Research Category:**

#### **A8. Therapeutic Intent**

Does this trial have therapeutic intent?

No

### **Section B: Exempt Request**

#### **B. Exempt From IRB Review**

Not Applicable

### **Section C: Background Information**

Worry and anxiety occur frequently among older adults (12%-15%) (Kessler et al., 2005; Byers et al., 2010). Even though these rates suggest higher prevalence of anxiety than depression, late-life anxiety has received significantly less attention. Clinically significant worry and associated disorders [generalized anxiety disorder (GAD) and anxiety otherwise specified (ADNOS)] are particularly common (Wolitzky-Taylor et al., 2010).

Most older adults with anxiety are unrecognized and undertreated (Calleo et al., 2009), thus increasing the potential for disability associated with both anxiety alone and co-occurring depression. Risk for inadequate recognition and care is particularly high for ethnic-minority elders in low-income, underserved communities (Brenes et al., 2008; Joo et al., 2010). Older adults, particularly minorities, prefer psychosocial treatments over medication for emotional difficulties (Givens et al., 2007). Cognitive behavioral treatment (CBT) produces positive outcomes for late-life worry/GAD in academic and primary care settings ([name] et al., 2009; Wetherell et al., 2007), but minorities are significantly under-represented in clinical trials (Office of the Surgeon General, 2009; Woodall et al., 2010), and standard CBT poorly addresses the needs of low-income minority older adults in underserved communities. In these settings, culturally tailored, person-centered interventions developed and tested in the context of solid community-clinical partnerships are needed to overcome barriers such as stigma, mistrust, racism, and misconceptions about symptoms and treatment. Integration with the faith-based community and incorporation of religious/spiritual (R/S) coping may be

particularly important in communities with high prevalence of African Americans (Blank et al., 2002; Lefler, 2009), where community life often centers on faith-based organizations and where individuals seek treatment/support from religious-spiritual leaders. More attention needs to be given to service delivery of anxiety treatments for underserved older adults.

Calmer Life (CL) is a culturally tailored, participant-centered research study that offers a skills-based intervention for late-life anxiety and includes other elements of care to meet the needs of underserved, minority older adults, including the option to integrate religion/spirituality, flexible delivery modes, and modular treatment format. This research study will not recruit participants from the VA. One of the study aims is to examine the feasibility and acceptability of a novel intervention in low-income and underserved communities. The VA does not have the infrastructure to reach the targeted population. Furthermore, through community recruitment, we will be able to reach Veterans, living in these low-income, underserved communities, who may or may not come to the VA for medical care. Finally, the prevalence of anxiety and depression is high among Veterans, and information gathered from this study will benefit older Veterans with anxiety and mood problems.

We are not enrolling participants at MEDVAMC in this study because it is focused on identifying people outside of a medical clinic or hospital settings who live in underserved, low-income communities. In addition, we have an ongoing trial of CBT for anxiety that did enroll veterans with VA Prime Care providers (H-23798) and completed a trial of CBT for anxiety and depression for home-based primary care patients at MEDVAMC (H-30655).

## Section D: Purpose and Objectives

The overall goals of the proposed research study are to: (1) examine quantitative outcomes in a well-conducted randomized clinical trial (RCT) of CL, relative to Enhanced Community Care (ECC), an information and referral intervention that represents care in a real-world community-service environment, and (2) evaluate implementation feasibility, which includes training community providers; examining program reach, engagement, acceptability, and barriers-facilitators; and preparing practical tools for replicating the program.

## Section E: Protocol Risks/Subjects

### E1. Risk Category

Category 1: Research not involving greater than minimum risk.

### E2. Subjects

Gender:

Both

Age:

Adult (18-64 yrs), Geriatric (65+ yrs)

Ethnicity:

All Ethnicities

Primary Language:

English

Groups to be recruited will include:

Patients

Which if any of the following vulnerable populations will be recruited as subjects?

Mentally ill

Vulnerable populations require special protections. How will you obtain informed consent, protect subject confidentiality, and prevent undue coercion?

Recruitment will be conducted via community outreach activities and referrals from social service and faith-based organizations. During community outreach events, information about the study will be provided in the form of verbal presentations or written summaries in brochures, community organization newsletters, or bulletins. Potential participants will provide their contact information if they want to be contacted by the study staff or they will contact the study staff directly. Study staff will review the informed consent form with potential participants in person and answer questions. We will not include participants with cognitive impairment, current suicidal intent, psychosis, mania or substance abuse within the past month. Further, we will train our research staff in the most responsible conduct of research including proper informed consent, confidentiality protection, and the avoidance of any coercion. To maintain confidentiality, every participant in the study will receive a unique ID number.

A separate VA release form will be used to communicate with the patient's health care provider(s) and any referring community agency provider if at any time the participant needs immediate treatment (eg, for suicidal intent, psychotic symptoms).

### **E3. Pregnant woman/fetus**

Will pregnant women and/or fetuses (as described in 45 CFR 46 Subpart B) be enrolled in the research?

No

### **E4. Neonates**

Will neonates of uncertain viability or nonviable neonates (as described in 45 CFR 46 Subpart B) be enrolled in the research?

No

### **E5. Children**

Will children be enrolled in the research?

No

anxiety/worry. Core modules occur during the first 3 sessions (education-awareness, motivational interviewing, deep breathing, self-statements). If participants desire to incorporate R/S, an R/S assessment occurs during session 2 to help the provider understand the participant's beliefs and practices. For subsequent sessions, participants select from elective modules with recommendations from the provider: progressive deep-muscle relaxation; cognitive restructuring; problem-solving; behavioral activation; and anxiety exposure. A sleep-management handout is available. R/S can be integrated into any module (e.g., R/S images or words in breathing and self-statements, increased R/S activities, emphasis on gratitude in thoughts/behaviors) or omitted entirely. Two separate workbooks are available. The last CL session is a review. During the second 3 months of CL, participants receive 3-4 follow-up calls to facilitate practice and continued use of skills, as well as evaluate ongoing functional and resource needs.

ECC is anchored in standard information and referral procedures and reflects a viable, real-world alternative to CL that will allow a critical comparison to inform implementation and policy. ECC includes information and referral for both mental health care and basic unmet needs along with brief telephone follow-up to discuss resources accessed and to evaluate any worsening of symptoms. ECC is provided over 6 months. Participants receive brief biweekly check-in calls for the first 6 weeks and then 1 brief check-in call 1 month later to inquire about access of community resources. During the second 3 months, ECC participants receive no more than one monthly phone call unless provider and supervisor determine that symptom severity warrants more frequent contact. At each call, providers will assess participants' ability to connect with identified resources, worsening of anxiety and depressive symptoms and need for crisis intervention. Participants will call project staff if symptoms worsen.

Outcome measures will be administered for participants in CL and ECC at baseline, 6 months, and 9 months as described in F.2.

#### Inclusion Criteria:

Inclusion criteria include 1) Age 50+; 2) significant worry as shown by a score of 50 or greater on the Penn State Worry Questionnaire (PSWQ); 3) must be English speaking; 4) must have a health care provider and provide written authorization to research team to communicate with this individual and any referring community agency provider; 5) must have access to a telephone, and 6) live, work, worship attend community functions, and/or receive health care in target geographic areas.

#### Exclusion Criteria:

Potential participants will be excluded only for conditions that threaten their and other's safety or those that preclude participation in the study. The exclusion criteria include 1) severe depression as indicated by a score of 20 or greater on the PHQ-9, 2) active suicidal intent, 3) psychosis, 4) bipolar disorder, 5) substance abuse within the last month, and 6) cognitive impairment indicated by 3 or fewer score on a six-item screener administered during initial assessment.

## F2. Procedure

Recruitment will be conducted via community outreach activities and referrals from partner social service and faith-based organizations. During community outreach events, information about the study will be provided in the form of verbal educational presentations or written project descriptions in brochures, community organization and church newsletters, or bulletins (Attached in Section S - Please see Calmer\_Life\_Flyer.pptx and Calmer Life Bulletin.docx). Potential participants will provide contact information to be called by the study staff or they will contact study staff directly. In order for potential participants to express interest and provide their contact information confidentially at public events, staff will distribute handouts that will include the two approved telephone anxiety screening questions (GAD-2) to allow participants to decide if the Calmer Life study would be appropriate for them (see Section S, "Calmer\_Life\_Interest Form.docx"). Any responses to these screening questions will not be used as study data, but will rather serve as informational tools to assist potential participants in deciding if the Calmer Life study may be appropriate for them. These potential participants will be asked two anxiety screening questions (GAD-2) on the phone as an initial screener, but participant responses will not be used as data. Responses will be used only to determine who will be invited to an in-person consent appointment.

All individuals who express interest in participation and respond affirmatively to one of the two screening questions will be scheduled for an in-person visit in a community setting or the participant's home, based on participant preference, to review the consent form, conduct a more formal screening, and obtain demographic information. Participants who provide written consent will complete a demographic information form, two anxiety screening measures (GAD-2), a six-item cognitive screener, the PSWQ and the PHQ-9. This will take

10 minutes. Participants who screen positive (respond affirmatively to at least one of two GAD-2 items), score four or more on the six-item cognitive screener, score 50 or more on the PSWQ and score less than 20 on the PHQ-9 will complete the Structured Clinical Interview for DSM-5 (SCID) in person or over the phone. All SCID interviews will be audiotaped and a random 10% will be rated by another project staff or investigator to assess interrater reliability. If a participant needs immediate treatment (e.g., suicidal intent, active psychotic symptoms), he/she will be referred for immediate psychiatric assistance following standard community-based emergency protocols, and the health care provider and any referring community provider will be contacted.

Excluded participants will receive a list of community resources. Participants who meet all inclusion criteria will complete a baseline telephone assessment. During baseline, the following measures will be administered via telephone: A separate VA release form will be used to communicate with the patient's health care provider (s) and any referring community agency provider if at any time the participant needs immediate treatment (ie, for suicidal intent, psychotic symptoms). Penn State Worry Questionnaire (PSWQ), Geriatric Anxiety Inventory (GAI-SF), Generalized Anxiety Disorder 7 (GAD-7), Patient Health Questionnaire (PHQ-9), Geriatric Depression Scale (GDS), Late-life Functional Disability Index (LL-FDI), Health-related Quality of Life (SF-12), Insomnia Severity Index (ISI), Service Use Questionnaire, and Utilization of Medications, PTSD Checklist for DSM-5 (PCL-5) and the Brief RCOPE. Upon completion of baseline assessment, participants will be assigned randomly to CL or ECC and will follow 6 months of procedures as described in Section F1. Assessments at 6 and 9 months will repeat the baseline measures, except for the Brief RCOPE, with the addition of the Client Satisfaction Questionnaire (CSQ). Participants who complete the CL intervention and are classified as low or high performers (maximum of 30 total) will be selected to complete qualitative interviews following completion of all outcome assessments. All assessments, qualitative interviews and intervention sessions will be recorded using the Olympus DS-5000id or DS-7000. Co-investigators will serve as supervisors to review integrity of randomly selected diagnostic and outcome assessments. Recordings from the CL and ECC sessions will be randomly selected for treatment integrity review by MEDVAMC psychologists on the research team who have expertise in the identification and treatment of late-life anxiety.

Telephone screening and appointment scheduling will be done at the MEDVAMC; however, MEDVAMC patients will not be recruited. Screening and diagnostic interviews will occur via telephone from VA leased space (IQUEST). Telephone-based study intervention sessions also will be conducted from IQUEST. All research activities at community settings also will be carried out by WOC or VA paid staff and investigators. BCM resources to be utilized include Office of Sponsored Programs and Department of Psychiatry grant administration, salaries paid via BCM to WOC employees and investigators with shared VA-BCM salary reimbursement ([name], [name], [name]), and BCM e-mail for communication with community providers and across investigators/staff who need to communicate at times when VA email access is unavailable.

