## Section G: Sample Size/Data Analysis

### G1. Sample Size

How many subjects (or specimens, or charts) will be used in this study?

Local: 300            Worldwide: 300

Please indicate why you chose the sample size proposed:

Effectiveness Aims. In our most recent primary care trial, we found moderate effect sizes for both primary ( $g = .40 - .50$ ) and secondary ( $g = .40 - .57$ ) measures. These effects are within the range of effect sizes reported for other trials of CBT and pharmacotherapy for late-life anxiety. Estimated sample sizes will be adjusted for study attrition, defined by failure to complete 6- and 9-month assessments. This team's prior studies have suggested study attrition ranging from 19% to 25%. Study attrition in our pilot community work is even lower (12%; H-30928.), potentially due to flexibility with regard to delivery options that minimize access barriers. Thus, we expect roughly 15% study attrition, but data analytic methods will employ multiple imputation procedures to use data from all participants. Study attrition will be minimized with provision of clear information about the project at the time of outreach and recruitment, the use of telephone-based assessments and person-centered treatment materials and procedures, and reminder calls. Reasons for withdrawal will be recorded. If differential study attrition occurs across groups, measures different by attrition status will be included as covariates in effectiveness outcome analyses. A 2-tailed type 1 error rate of 0.05 was used to calculate sample size. With 64 participants per group (total = 128), we will have 80% power to detect moderate group differences ( $d = .50$ ) in primary and secondary outcomes. Given potential attrition of 15%, we will randomize 150 subjects (75/group). Exclusion rates in prior studies have been 50% or greater

(H-23798, H-30928), which means we will need to enroll at least 300 participants in order to include and randomize 150. Implementation Aims. A purposive sampling strategy will be used for the qualitative interviews targeting CL participants defined as high and low performers. In qualitative research, sampling is completed when categories are saturated (ie, when the targeted group no longer provides new information). No more than 15 interviews are expected from each CL subset (high- and low-performing participants; maximum 30 participant interviews).

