**Specific Aim 3.** Examine the maintenance of outcomes in CL and ECC. Analyses for all primary and secondary outcomes will be repeated to examine treatment differences in outcomes at 9 months. All procedures will be as previously described.

**Analysis of Implementation Potential.** Differences in satisfaction between CL and ECC at 6 and 9 months will be examined with either an independent samples t-test or ANCOVA (if covariates are warranted). Descriptive data that address reach, participant initiation and engagement, and treatment fidelity will be reviewed by the CLC. CLC input will be used to modify the model of care if needed and to develop implementation strategies. Participant representativeness (vs. excluded participants and partner caseloads) will be examined with chi-square tests (ordinal variables) and independent sample t-tests (interval variables).

Qualitative data will be analyzed with framework analysis, whereby themes generating from both a priori issues and data are identified. Digital recordings of each qualitative interview will be transcribed verbatim into text. Transcripts will be imported into Atlas.ti to facilitate storing, management, and visualization. First, we will check transcripts for accuracy. Then, all data will be analyzed, and contact summary sheets completed after each interview, to establish a thematic framework. Raters will compare coding across transcripts and discuss/reconcile dissimilar coding. From the categories, themes within and across groups will be identified. Data analysis will identify recurring and important themes regarding acceptability, facilitators, and barriers. Descriptive statistics will characterize demographic data.

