## Section L: Cost/Payment

Delineate clinical procedures from research procedures. Will subject's insurance (or subject) be responsible for research related costs? If so state for which items subject's insurance (or subject) will be responsible (surgery, device, drugs, etc). If appropriate, discuss the availability of financial counseling.

All evaluation and treatment procedures will be offered at no cost to the subjects other than travel to study sites. Participants will be reimbursed \$25.00 via gift card for each telephone assessment and qualitative interview completed.

If subjects will be paid (money, gift certificates, coupons, etc.) to participate in this research project, please note the total dollar amount (or dollar value amount) and distribution plan (one payment, pro-rated payment, paid

upon completion, etc) of the payment.

Dollar Amount:

25

Distribution Plan:

All participants will receive a \$25.00 gift card for each telephone assessment completed at baseline, 6 and 9 months. Participants who complete the CL intervention may be selected to complete an additional qualitative interview for which they will also receive a \$25.00 gift card. CL participants may receive a total of \$100 in gift cards and and ECC participants may receive a total of \$75.00 in gift cards.

Gift cards will be mailed to participants by the study coordinator.

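### Qualitative interviews are limited to people who complete CL, a term left undefined, so themes on barriers and acceptability are likely to under-represent what stops people from starting or finishing

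*Combined protocol and SAP*

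**What the plan says.** F2 (Procedure) states who is interviewed: "Participants who complete the CL intervention and are classified as low or high performers (maximum of 30 total". It also sets the timing. These people "will be selected to complete qualitative interviews following completion of all outcome assessments", and the last assessment is at 9 months. Section L (Cost/Payment) repeats the condition: "Participants who complete the CL intervention may be selected to complete an additional qualitative interview".

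G1 (Sample Size, Implementation Aims) gives the frame without it: "A purposive sampling strategy will be used for the qualitative interviews targeting CL participants defined as high and low performers". G1 adds that "No more than 15 interviews are expected from each CL subset", and that sampling ends when the targeted group yields nothing new.

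The interviews serve the second goal in Section D, implementation feasibility, which covers "examining program reach, engagement, acceptability, and barriers-facilitators". G2 (Data Analysis) says of the transcripts: "Data analysis will identify recurring and important themes regarding acceptability, facilitators, and barriers".

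No section defines completing CL, or high or low performer. F1 lets participants choose their number of sessions in the first 3 months, up to 12, with 6 as a recommended minimum. For people who leave, G1 has reasons for withdrawal recorded. G2 has descriptive data on reach, initiation, engagement and fidelity reviewed by the CLC, and compares study completers with noncompleters at baseline.

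**The concern.** The interviews are meant to find out what makes CL acceptable and what gets in its way. Someone who never started, or who stopped because of a barrier, has direct knowledge of it. F2 joins completion and performer status with an *and*, so a low performer must also have completed. Nothing in the document provides for interviewing anyone else in the CL arm.

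Saturation does not repair this. G1 judges it within the targeted group, so saturation among completers says nothing about themes that only non-completers would raise. What is at stake is how complete the barrier and acceptability findings are, and through them the advice on replication. The treatment comparison is not at stake.

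**Working it through.** **1. The plan's own figures.** For the trial as a whole, G1 uses d = 0.50, two-sided alpha 0.05 and 80% power. A two-sample t-test needs 63.8, so 64 per group, with power 0.801 at 64. Allowing for 15% attrition, 64 / (1 − 0.15) = 75.3, against 75 stated; the difference is immaterial. For the interviews, 15 + 15 = 30, which agrees with the maximum in F2. That number rests on saturation and has no formula to check.

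**2. The frame, section by section.**
- F2: completed CL, and classified as a low or high performer; interviewed after all outcome assessments.
- Section L: completed CL; performer status not mentioned.
- G1: CL participant and high or low performer; completion not mentioned.

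The narrowest text is F2. Read together, the three sections exclude non-completers. Read alone, G1 would admit a non-completer who counts as a low performer, but it does not say that such people will be approached.

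**3. Who is left out under F2.** People who never start CL, and people who stop short of whatever counts as completion. The boundary of the second group cannot be drawn from the document, because participants choose how many sessions to have.

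**4. Size, under an assumption.** The documents give no CL non-completion rate. The nearest figures, all in G1, are for study attrition, defined as failure to complete the 6- and 9-month assessments: 12% in the community pilot, 15% planned, and 19% to 25% in the team's earlier studies. Assume that the non-completion rate r equals study attrition. The number outside the frame is then 75 × r. As a benchmark only, since the sampling is purposive, 30 people drawn in proportion from all 75 would include 30 × r of them.

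| r | Outside frame, 75 × r | In frame | Proportional share, 30 × r | F2 rule |
|---|---|---|---|---|
| 12% | 9.0 | 66 | 3.6 | 0 |
| 15% | 11.25, about 11 | 64 | 4.5 | 0 |
| 19% | 14.25, about 14 | 61 | 5.7 | 0 |
| 25% | 18.75, about 19 | 56 | 7.5 | 0 |

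**The case against.** The strongest reply is that the plan already leans against favourable selection. Up to 15 of the 30 interviews go to low performers. With completion undefined and the number of sessions chosen by the participant, someone who attended only a few may count as a completer. This stands in part: it cannot be said that everyone who stops early has no chance of an interview. It does not help non-starters, or anyone judged not to have completed, and it depends on definitions that the plan does not give.

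Second, other sources cover people who do not stay: withdrawal reasons, the reach, initiation and engagement data, and the comparisons with noncompleters, excluded people and partner caseloads. A reader might infer that the replication tools would rest on completers alone. G2 does not support that, because CLC input on the descriptive data also feeds the implementation strategies. These sources are thinner than interviews, however, and the thematic analysis uses interview transcripts.

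Third, the attrition figures measure something else. A person can complete CL and miss an assessment, or stop CL and attend both. A reader might take the 11 (or up to 19) expected study dropouts as the people shut out. The completion rule does not imply that. The timing rule might also exclude some who miss an assessment, but F2 does not say how they are handled. The figures serve only as a stated proxy.

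Fourth, interviewing after the last assessment has a purpose. It keeps an extra contact, made in one arm only, out of the period before the outcomes are measured. This stands, and the fix respects it.

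Finally, G1 can be read as the general statement and F2 as the specific one, so the difference between them is mild. It still needs one wording, because staff must know whom to approach.

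**Conclusion.** The point holds as a weakness of the implementation component that should be corrected. Under F2 and Section L, people randomised to CL who do not start or do not complete it are outside the interview frame, and the themes are likely to under-represent the barriers that stop people. The number affected is about 9 to 19 of 75, or 11 at the planned 15%, only if CL non-completion equals study attrition; the true rate is not given.

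A reader might go further and conclude that the findings will be favourably biased. That direction is expected but not demonstrated. The interviews are purposive and thematic, they estimate no prevalence, and the documents offer nothing from which to size a bias. The comparisons of CL with ECC in Aims 1 to 3 are not affected.

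**What to change.** - Define the interview frame as everyone randomised to CL, and use the same wording in F2, G1 and Section L.
- Define completion of CL, and high and low performer, before anyone is selected.
- Within the maximum of 30, reserve a stated part of the 15 low-performer places for non-starters and non-completers.
- For those still in follow-up, including people who stopped CL, keep the interview after the 9-month assessment, so that no CL-only contact is added before outcomes are measured. Interview those who leave the study earlier only if they agree to that contact.
- Report how many non-starters and non-completers were approached and how many were interviewed.

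The cap and the gift-card budget do not change: 30 × $25 = $750 at most. The costs are the edits to three sections, more effort to reach people who may decline or be hard to find, and some interviews of completers given up. Keeping the late timing also means that barriers met in the first 3 months are recalled about 9 − 3 = 6 months later or more. The change should be made before interviews begin, because this information is hard to recover once people have left.
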